9.4.8 Treatment Compliance

Records of treatment compliance for each subject will be kept during the Treatment Period. CRAs will review treatment compliance during site visits and at the completion of the study.

9.4.9 Drug Supplies and Accountability

In compliance with local regulatory requirements, drug supplies will not be sent to the investigator (or if regionally required, the head of the medical institution or the designated pharmacist) until the following documentation has been received by the sponsor:

- A signed and dated confidentiality agreement
- A copy of the final protocol signature page, signed and dated by both the sponsor and investigator

- Written proof of approval of the protocol, the ICFs, and any other information provided to the subjects by the IRB/IEC for the institution where the study is to be conducted
- A copy of the IRB/IEC-approved ICF and any other documentation provided to the subjects to be used in this study
- The IRB/IEC membership list and statutes or Health and Human Services Assurance number
- A copy of the certification and a table of the normal laboratory ranges for the reference laboratory conducting the clinical laboratory tests required by this protocol
- An investigator-signed and dated FDA Form FDA 1572, where applicable
- Financial Disclosure form(s) for the principal investigator and all subinvestigators listed on Form FDA 1572, where applicable
- A signed and dated curriculum vitae of the principal investigator including a copy of the principal investigator's current medical license (required for United States sites) or medical registration number on the curriculum vitae
- A signed and dated Clinical Trial Agreement (CTA)
- A copy of the regulatory authority approval for the country in which the study is being conducted (if required), and the Import License (if required)

The investigator and the study staff (or if regionally required, the head of the medical institution or the designated pharmacist) will be responsible for the accountability of all study drugs (dispensing, inventory, and record keeping) following the sponsor's instructions and adherence to GCP guidelines as well as local or regional requirements.

Under no circumstances will the investigator allow the study drugs to be used other than as directed by this protocol. Study drugs will not be dispensed to any individual who is not enrolled in the study.

The site must maintain an accurate and timely record of the following: receipt of all study drugs, dispensing of study drugs to the subject, collection and reconciliation of unused study drugs that are either returned by the subjects or shipped to site but not dispensed to subjects, and return of reconciled study drugs to the sponsor or (where applicable) destruction of reconciled study drugs at the site. This includes, but may not be limited to: (a) documentation of receipt of study drugs, (b) study drugs dispensing/return reconciliation log, (c) study drugs accountability log, (d) all shipping service receipts, and (e) documentation of returns to the sponsor. All forms will be provided by the sponsor. Any comparable forms that the site wishes to use must be approved by the sponsor.

The study drugs and inventory records must be made available, upon request, for inspection by a designated representative of the sponsor or a representative of a health authority (eg, FDA, Medicines and Healthcare Regulatory Agency). As applicable, all unused study drugs and empty and partially empty containers from used study drugs are to be returned to the investigator (or if regionally required, the head of the medical institution or the designated pharmacist) by the subject and, together with unused study drugs that were shipped to the site

but not dispensed to subjects, are to be returned to the sponsor's designated central or local depot(s) during the study or at the conclusion of the study, unless provision is made by the sponsor for destruction of study drugs and containers at the site. Destruction at the site will only occur under circumstances where regulation or supply type prohibits the return of study drugs to the central or local depot(s). Approval for destruction to occur at the site must be provided by the sponsor in advance. Upon completion of drug accountability and reconciliation procedures by the site's personnel and documentation procedures by the sponsor's personnel, study drugs that are to be returned to the sponsor's designated central or local depot(s) must be boxed, sealed, and shipped back to the central or local depot(s) following all local regulatory requirements. In some regions, study drugs may be removed from the site and hand delivered to the central or local depot by sponsor representatives. Where study drugs are approved for destruction at the site, destruction will occur following the site's standard procedures and certificates of destruction will be provided to the sponsor.

Drug accountability will be reviewed during site visits and at the completion of the study.

9.5 Study Assessments

9.5.1 Assessments

9.5.1.1 Demography

Subject demography information will be collected at the Screening Visit. Demography information includes date of birth (or age), sex, race/ethnicity, native language, handedness, and highest education level.

9.5.1.2 Baseline Assessments

Assessments to be made at Screening and Baseline and throughout the study are described in [Section 9.5.1.3](#), [Section 9.5.1.4](#), and [Section 9.5.1.5](#).

9.5.1.2.1 MEDICAL HISTORY AND PHYSICAL EXAMINATIONS

Medical and surgical history, current medications including AChEI and memantine use, and current medical conditions will be recorded at the Screening Visit. All medical and surgical history within 10 years must be noted in the Medical History and Current Medical Conditions eCRF. Medical history will include history of cognitive impairment due to AD. Subjects will be asked about history of TB, infections due to varicella zoster virus (chickenpox and herpes zoster/shingles) and HSV Types 1 and 2 (orolabial herpes/cold sores and genital herpes, respectively). The medical history of such infections will include onset, duration, relapse frequency, severity, and treatments. Subjects will also be asked about their vaccination history including vaccinations against varicella zoster virus and TB. The 15-item GDS and modified Hachinski ischemic scale will also be assessed at Screening as part of the exclusion criteria.

Physical examinations (complete or routine) will be performed as designated in [Table 6](#). A complete physical examination will include evaluations of the head, eyes, ears, nose, throat,

neck, chest (including heart and lungs), abdomen, limbs, and skin, and a neurological examination. A urogenital examination will only be required in the presence of clinical symptoms related to this region. Documentation of the physical examination will be included in the source documentation at the site. Significant findings at the Screening Visit will be recorded on the Medical History and Current Medical Conditions eCRF. Changes from screening physical examination findings that meet the definition of an AE will be recorded on the Adverse Events eCRF.

9.5.1.2.2 VIRAL TESTING

As specified in [Table 6](#), blood will be collected for screening for Hepatitis B and Hepatitis C for determining eligibility, and at Baseline for viral characterization.

9.5.1.2.3 B12 TESTING

Blood will also be collected for vitamin B12 levels as specified in [Table 6](#).

9.5.1.2.4 TB EXPOSURE TESTING

Blood will also be collected for testing for previous TB exposure, as specified in [Table 6](#).

9.5.1.2.5 URINE DRUG TESTING

Urine will be collected for drug screening as specified in [Table 6](#).

9.5.1.3 Efficacy Assessments

9.5.1.3.1 PSYCHOMETRIC ASSESSMENTS

The timing of psychometric assessments is shown in [Table 6](#) and [Table 7](#). These assessments should be administered in the morning (or, if not possible, consistently at the same time of day) and should be completed before more invasive assessments or procedures (eg, physical examination, ECG, blood draws). The order of assessments is: MMSE, CDR, FAQ, ISLT (immediate recall), CBB, and ISLT (delayed recall) at Screening; and MMSE, CDR, ADAS-cog₁₄, FAQ, ISLT (immediate recall), CBB, and ISLT (delayed recall) at the Baseline Visit.

At visits where the CDR or FAQ are conducted, the investigator will determine whether the caregiver or informant must attend in person or whether telephone contact will be suitable, and will base this determination upon the functional ability of the subject among other factors.

The Derived Alzheimer's Disease Composite Score: The primary efficacy endpoint is the change from baseline in the derived ADCOMS at 18 months of treatment in MCI/Prodromal subjects.

The ADCOMS is derived from the ADAS-cog (4 items), the MMSE (2 items), and the CDR (all 6 items), described below. The ADCOMS is more sensitive to clinical progression

compared with currently existing clinical batteries and requires smaller sample sizes for clinical studies in MCI/Prodromal AD or mild to moderate AD. (revised per Amendment 01) It also shows sensitivity to treatment effects with AChEIs. The ADCOMS assesses both cognitive and functional domains and can be offered as a single primary clinical endpoint. The ADCOMS has a range from 0 to 1.97.

CogState Brief Battery: The CBB is a computer-based battery comprising 4 cognitive tests:

1. Detection – a simple reaction time test where the subject presses a key when the card is turned face up from a pack of cards (“Has the card turned over”). Speed of response is the measure.
2. Identification – a simple choice reaction time test where the subject presses 1 of 2 keys when the card just turned face up is either a red card or a black card (“Is the card red”). Speed of response is the measure.
3. One Card Back – a simple working memory test where the subject presses 1 of 2 keys when the card turned face up is either the card seen in the immediately previous trial or not (“Is the previous card the same”). Accuracy of response is the measure.
4. One Card Learning – a visual learning and memory test where the subject presses 1 of 2 keys depending on whether the card just turned face up has been seen before or not in the task (“Have you seen this card before in this task”). Accuracy of response is the measure.

ISLT: The ISLT is a verbal learning and episodic memory test assessing both immediate and delayed recall. Subjects are read a list of 12 items that can be obtained at the local shopping center. Subjects are asked to recall as many of the items as possible and this immediate recall trial is repeated 3 times. After a delay of approximately 15 minutes, in which time the CBB is performed, subjects are again asked to recall as many of the words on the shopping list as they can (ie, a delayed recall trial).

Mini Mental State Examination: A 30-point scale that measures orientation to time and place, registration, immediate and delayed recall, attention, language, and drawing. Scores range from 0 (most impaired) to 30 (no impairment).

Clinical Dementia Rating: The CDR assesses 6 domains of subject function; memory, orientation, judgment and problem solving, community affairs, home and hobbies and personal care. Each of these items has a maximum possible score of 3 points and the total score is a sum of the item scores (sum of boxes) giving a total possible score of 0 to 18 with higher scores indicating more impairment.

Alzheimer's Disease Assessment Scale - cognitive subscale: Discussed in [Section 9.2.4](#).

Functional Assessment Questionnaire: Either a caregiver or informant or the subject provides performance ratings (from 0 to 3) on 10 complex activities of daily living performed within the preceding 4 weeks. Scores range from 0 (independent) to 30 (dependent).

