- a. Subjective Memory Complaint with evidence of concern about a decline in cognition from the subject, informant, or clinician's observation
 - b. Cognitive impairment of at least 1 SD from age adjusted norms in delayed recall on the ISLT
 - c. FAQ ≤ 24 (revised per Amendment 01)
 - d. MMSE ≥ 16 (revised per Amendment 01)
2. Amyloid positive PET image based on centralized PET scan reading
 3. Male or female, age 50 to 85 years, inclusive at time of consent
 4. Must have an identified caregiver or informant who is willing and able to provide follow-up information on the subject throughout the course of the study. This person must, in the opinion of the investigator, spend sufficient time with the subject on a regular basis such that the caregiver or informant can reliably fulfill the study requirements and must provide separate written consent. The caregiver or informant need not be living in the same residence as the subject. If the caregiver or informant is not residing with the subject, the investigator has to be satisfied that the subject can contact the caregiver or informant readily during the times when the caregiver or informant is not with the subject. If in doubt about whether a subject's care arrangements are suitable for inclusion, the investigator should discuss this with the medical monitor. At visits where the CDR or FAQ are conducted, caregivers or informants need to either attend the visit in person along with the subject or be able to be contacted by telephone at the time of the visit. The investigator will determine whether attendance in person is required or whether telephone contact will be suitable and will base this determination upon the functional ability of the subject among other factors.
 5. If receiving acetylcholinesterase inhibitors (AChEIs) or memantine, must have been on a stable dose for at least 12 weeks before the baseline cognitive assessments at Visit 2, with no plans for dose adjustment in the foreseeable future. Treatment-naïve subjects can be entered into the study but there should be no plans to initiate treatment with AChEIs or memantine at the time of entry into the study.
 6. Must have been on stable doses of all other permitted chronically used concomitant medications (ie, not related to their cognitive decline) for at least 4 weeks before randomization.

Exclusion Criteria

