2. Identification – a simple choice reaction time test. Speed of response is the measure.
3. One Card Back – a simple working memory test. Accuracy of response is the measure.
4. One Card Learning – a visual learning and memory test. Accuracy of response is the measure.

International Shopping List Task: The ISLT is a verbal learning and episodic memory test assessing both immediate and delayed recall.

Functional Assessment Questionnaire: The FAQ has 10 items concerned with performing daily tasks necessary for independent living. Either a caregiver or informant or the subject provides performance ratings on 10 complex activities of daily living performed within the preceding 4 weeks.

Volumetric Magnetic Resonance Imaging: vMRI will be used to evaluate disease modification, including the change from Baseline in terms of the measured hippocampal volume based upon the centralized measurement of the structure on repeated MRIs.

Pharmacokinetic Assessments

Blood and CSF samples will be collected for the determination of the concentrations of E2609. Analyses of metabolite concentrations may be performed depending on emerging data from other studies with E2609.

Pharmacodynamic, Pharmacogenomic and Other Biomarker Assessments

Brain atrophy will be measured by vMRI: see Efficacy Assessments (above).

The soluble biomarkers $A\beta(1-x)$, $A\beta(1-42)$, total tau (t-tau), and p-tau will be measured in CSF. BACE1 levels and activity in CSF will also be measured. Other exploratory biomarkers (eg, miRNA) may also be evaluated in plasma and/or CSF.

Amyloid PET imaging will be used to confirm that all subjects eligible for progression to the

Baseline Period have amyloid deposition in the brain. Longitudinal amyloid PET imaging will also be conducted after 18 months of treatment (or at ED, providing the subject has received at least 39 weeks of study drug). Longitudinal amyloid PET imaging will only be conducted through to the time at which acceptable 18-month PET scans have been obtained for at least 25 subjects per treatment arm for each amyloid PET ligand used.

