9.3.1 Inclusion Criteria

Subjects must meet all of the following criteria to be included in this study:

1. Meets the core clinical research criteria of the NIA-AA for MCI due to AD ([Albert, et al., 2011](#)) or AD dementia ([McKhann, et al., 2011](#)) and is "staged" or classified as either MCI or mild to moderate dementia and also complies with the following: (revised per Amendment 01)

Required at both Screening and Baseline:

- a. Subjective Memory Complaint with evidence of concern about a decline in cognition from the subject, informant, or clinician's observation
 - b. Cognitive impairment of at least 1 SD from age adjusted norms in delayed recall on the ISLT
 - c. FAQ \leq 24 (revised per Amendment 01)
 - d. MMSE \geq 16 (revised per Amendment 01)
2. Amyloid positive PET image based on centralized PET scan reading
 3. Male or female, age 50 to 85 years, inclusive at time of consent
 4. Must have an identified caregiver or informant who is willing and able to provide follow-up information on the subject throughout the course of the study. This person must, in the opinion of the investigator, spend sufficient time with the subject on a regular basis such that the caregiver or informant can reliably fulfill the study requirements and must provide separate written consent. The caregiver or informant need not be living in the same residence as the subject. If the caregiver or informant is not residing with the subject, the investigator has to be satisfied that the subject can contact the caregiver or informant readily during the times when the caregiver or informant is not with the subject. If in doubt about whether a subject's care arrangements are suitable for inclusion, the investigator should discuss this with the medical monitor. At visits where the CDR or FAQ are conducted, caregivers or informants need to either attend the visit in person along with the subject or be able to be contacted by telephone at the time of the visit. The investigator will determine whether attendance in person is required or whether telephone contact will be suitable and will base this determination upon the functional ability of the subject among other factors.

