9.7.1.1.3 EXPLORATORY ENDPOINTS

(revised per Amendment 01)

Change from baseline in:

- The derived ADCOMS at 12 months of treatment in MCI/Prodromal and mild to moderate AD subjects
- Total hippocampal volume at 12 and 18 months of treatment in mild to moderate AD subjects as measured by vMRI
- CSF A β (1-42) after 4 weeks and 18 months of treatment in MCI/Prodromal subjects
- CSF A β (1-x) and A β (1-42) after 4 weeks and 18 months of treatment in mild to moderate AD subjects
- The following clinical assessments at 12 weeks and at 6, 9, 12, 15, 18, 19, and 21 months: ADAS-cog, CDR, MMSE, ISLT, CBB, and FAQ in MCI/Prodromal and mild to moderate AD subjects
- CSF biomarkers of neurodegeneration (eg, tau and p-tau) at 18 months of treatment in MCI/Prodromal and mild moderate AD subjects
- Plasma and CSF amyloid, and CSF BACE1 measurements after 4 weeks and 18 months of treatment, and during posttreatment follow-up in MCI/Prodromal and mild moderate AD subjects
- Left and right hippocampal, whole brain, and total ventricular volume at 6, 12 and, 18 months in MCI/Prodromal and mild to moderate AD subjects as measured by vMRI
- Brain amyloid levels as measured by amyloid PET at 18 months in MCI/Prodromal and mild to moderate AD subjects
- The population PK parameters of E2609 including the effect of intrinsic and extrinsic factors (including *NAT2* phenotype) in MCI/Prodromal and mild to moderate AD subjects

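### The FAQ may be rated by the informant or by the memory-impaired subject, with no rule to keep the rater constant, which can add avoidable rater noise to an entry check and an exploratory endpoint

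*Protocol*

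**What the plan says.** Section 9.5.1.3.1 describes the FAQ as 10 items scored 0 to 3 with a 4-week recall period. On who answers, it says: "Either a caregiver or informant or the subject provides performance ratings (from 0 to 3) on 10 complex activities of daily living". The Efficacy Assessments part of the synopsis gives the same choice: "Either a caregiver or informant or the subject provides performance ratings on 10 complex activities of daily living".

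The FAQ has three uses in the protocol:
- **Entry limit.** Inclusion criterion 1 (section 9.3.1) requires a score of 24 or less at both Screening and Baseline.
- **Baseline variable.** Section 9.7.1.4 summarises it by treatment group.
- **Exploratory endpoint.** Section 9.7.1.1.3 lists change from baseline at 12 weeks and at 6, 9, 12, 15, 18, 19 and 21 months for "ADAS-cog, CDR, MMSE, ISLT, CBB, and FAQ in MCI/Prodromal and mild to moderate AD subjects". Section 9.7.1.6.3 analyses this by MMRM.

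On the informant, inclusion criterion 4 opens: "Must have an identified caregiver or informant who is willing and able to provide follow-up information on the subject throughout the course of the study". For visits with a CDR or FAQ it adds that "caregivers or informants need to either attend the visit in person along with the subject or be able to be contacted by telephone". Sections 9.1.1.1 and 9.1.1.2 also call for the informant's presence at Screening and at Baseline.

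**The concern.** Every subject must show memory impairment to enter: "Cognitive impairment of at least 1 SD from age adjusted norms in delayed recall on the ISLT". MMSE may be as low as 16. The protocol nevertheless allows such a subject to recall and rate ten complex daily activities over the past 4 weeks, and it lets the rater differ from one visit to the next.

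Two uses are exposed. At entry, the score compared with the limit of 24 may depend on who answered. After baseline, if the rater changes, any difference between raters goes into the change score and cannot be told apart from a change in function. Section 9.2.4 values the FAQ as a marker of clinical meaning because it reflects functional state, so it is worth measuring the same way each time.

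This is a rule the protocol states, not a detail left to the analysis plan. An analysis plan cannot recover who answered if the rater was neither fixed nor recorded.

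**Working it through.** The protocol states no figure for a rater effect, so there is none to reproduce. The check is a comparison of passages plus a short argument in symbols.

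**1. Scale.** 10 items × 3 points = 30, which agrees with the stated range of 0 to 30.

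**2. Is the rater fixed anywhere?**

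| Place | What it settles | Names the FAQ rater? | Requires the same rater? |
|---|---|---|---|
| Synopsis and 9.5.1.3.1, FAQ description | Informant or subject may rate | Leaves it open | No |
| 9.3.1, criterion 4 | Informant identified for the whole study and available at CDR/FAQ visits | No | No |
| 9.1.1.1 and 9.1.1.2 | Informant present at Screening and Baseline | No | No |
| 9.5.1.3.1, opening paragraphs; Table 6 note d; Table 7 note p | Order, time of day, in person or by telephone | No | No |

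The informant provisions make someone available. They do not assign the FAQ to that person or remove the subject as an option.

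**3. Contrast with other measures.** The CDR involves interviewing both subject and informant (9.2.4). Blood pressure is taken on the same arm and preferably by the same person (9.5.1.5.4). The PET tracer is fixed within a subject (Table 7 note r). The FAQ rater has no comparable rule.

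**4. Entry check.** The cap is a sharp cut. A subject whom one rater would score 25 and the other 24 is excluded or admitted according to who answers. The documents do not say which rater tends to score higher, or by how much.

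**5. Change from baseline.** Let d be the average difference between raters, and let p be the proportion of an arm whose rater switches after baseline, with all switches in the same direction.
- Shift in one arm's mean change = p × d.
- Shift in the active-minus-placebo contrast = (p for active − p for placebo) × d, if d is the same in both arms.
- If the two proportions are equal, the contrast shifts by 0 × d = 0, and what remains is extra variability.

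Neither p nor d is in the documents, so the expressions cannot be evaluated.

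**6. What is not affected.** ADCOMS is built from ADAS-cog, MMSE and CDR items (9.5.1.3.1). The primary endpoint (9.7.1.1.1) and secondary endpoints (9.7.1.1.2) do not use the FAQ. The interim analyses that drive stopping and adaptive allocation run on ADCOMS (9.7.3).

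**The case against.** The strongest case against is that the consequence is small and the mechanism unproven.

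- **Entry.** The informant is to be present at both visits that apply the limit, and site staff interview subject and informant together at Screening (9.1.1.1). MMSE, NIA-AA criteria and the clinician's classification also apply. This largely stands. A reader might infer that self-rating would regularly admit subjects who are too impaired, but nothing in the documents shows that subjects near the cap would be self-rated, or that self-rating scores lower.
- **Endpoint.** FAQ change is exploratory, and no success, futility or allocation rule depends on it. This stands in full.
- **Bias.** In a randomised, double-blind comparison, switching that is equal across arms cancels from the contrast. If switching follows decline and there is no treatment effect, decline and switching are equal across arms on average. The mechanism could then distort the size of a real difference but would not create one. This stands.
- **Mechanism.** A reader might infer that the rater will move from subject to informant as disease advances. That is plausible, but the protocol does not say it, and an identified informant available throughout points towards stability.
- **Detail elsewhere.** Rater training or CRF Completion Guidelines might fix the rater. They are not shown, and the explicit either/or wording would still contradict such a rule.
- **Version.** The text belongs to Version 3.0 (Amendment 01). A copy of Appendix 2, Listing 2 marked with Amendment 02 shows that a later version exists, and its body is not shown. The Version 2.0 synopsis carries the same sentence, so Amendment 01 left it as it was, but a later correction cannot be excluded.

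What survives is that the text shown permits either rater, fixes neither, and gives no reason for a choice that criterion 4 makes unnecessary.

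**Conclusion.** The point holds as a cheap improvement in measurement. In the Version 3.0 text, the FAQ may be answered by the informant or by a memory-impaired subject, and the rater need not stay the same. This can add noise to the FAQ ≤24 check and to the exploratory FAQ change scores at 8 post-baseline time points. It would bias a between-arm comparison only if switching differed by arm, as it might if switching tracked progression and progression differed.

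No size is given because the documents supply neither the rater difference nor a switching rate. A reader might be tempted to multiply assumed values of the two. The product would be a within-arm shift, not the planned comparison with placebo, and it would rest entirely on the assumptions.

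The conclusion assumes that no unseen rater manual or later protocol version already fixes the rater.

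**What to change.** In section 9.5.1.3.1 and in the synopsis, delete *or the subject* from the FAQ description and state that:
- the FAQ is rated by the caregiver or informant identified under inclusion criterion 4;
- the same informant rates it at Screening, Baseline and all later visits where possible;
- the rater, and any change of rater, is recorded on the eCRF.

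First check the wording in the latest protocol version, in case it has already been corrected.

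The cost is two edits to the text and one eCRF item. No new visit, person or procedure is needed, because the informant must already attend or be reachable by telephone. The downside is an occasional missing FAQ when the informant cannot be reached.
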